5.2 Subject Exclusion Criteria

The subject must be excluded from participating in the trial if the subject:

1. Has evidence of leptomeningeal disease on MRI or in CSF.
2. If tumor demonstrates EGFR or ALK genomic tumor aberrations, subject should have documented disease progression on FDA-approved therapy for these aberrations.
3. Has a diagnosis of immunodeficiency and is not on continuous daily immunosuppressive therapy within 7 days prior to the first dose of trial treatment. (Subjects may receive steroids before or after SRS to prevent or manage cerebral edema; inhalational steroids are permitted)
4. Has previously progressed on a PD-1 or PD-L1 checkpoint inhibitor for systemic disease.
5. Has a known history of active TB (Bacillus Tuberculosis)
6. Has hypersensitivity to pembrolizumab, or ferumoxylol or any of their excipients.
7. Has had a prior anti-cancer monoclonal antibody (mAb) within 4 weeks prior to study Day 1 or who has not recovered (i.e., ≤ Grade 1 or at baseline) from adverse events due to agents administered more than 4 weeks earlier.
 - a. Note: The use of Denosumab is an exception to this criterion.
8. Subject who has not recovered (i.e., ≤ Grade 1 or at baseline) from adverse events due to a previously administered agent.
 - a. Note: Subjects with ≤ Grade 2 neuropathy are an exception to this criterion and may qualify for the study.
 - b. Note: Subjects with ≤ Grade 2 hematologic toxicities are an exception to this criterion and may qualify for the study.
 - c. Note: Subjects with ≤ Grade 2 fatigue are an exception to this criterion and may qualify for the study.
9. Has a known additional malignancy that is progressing or requires active treatment. Exceptions include basal cell carcinoma of the skin or squamous cell carcinoma of the skin that has undergone potentially curative therapy or in situ cervical cancer.
10. Has active autoimmune disease that has required systemic treatment in the past 2 years (i.e. with use of disease modifying agents, corticosteroids or immunosuppressive drugs). Replacement therapy (eg., thyroxine, insulin, or physiologic corticosteroid replacement therapy for adrenal or pituitary insufficiency, etc.) is not considered a form of systemic treatment.
11. Has known history of, or any evidence of active, non-infectious pneumonitis.
12. Has an active infection requiring systemic therapy.
13. Has a history or current evidence of any condition, therapy, or laboratory abnormality that might confound the results of the trial, interfere with the subject's participation

- for the full duration of the trial, or is not in the best interest of the subject to participate, in the opinion of the treating investigator.
14. Has known psychiatric or substance abuse disorders that would interfere with cooperation with the requirements of the trial.
 15. Is pregnant or breastfeeding, or expecting to conceive or father children within the projected duration of the trial, starting with the pre-screening or screening visit through 120 days after the last dose of trial treatment.
 16. Has a known history of Human Immunodeficiency Virus (HIV) (HIV 1/2 antibodies).
 17. Has known active Hepatitis B (e.g., HBsAg reactive) or Hepatitis C (e.g., HCV RNA [qualitative] is detected).
 18. Has received a live vaccine within 30 days of planned start of study therapy.
 - a. *Note: Seasonal influenza vaccines for injection are generally inactivated flu vaccines and are allowed; however intranasal influenza vaccines (e.g., Flu-Mist®) are live attenuated vaccines, and are not allowed.*
 19. Subjects with clinically significant signs of uncal herniation, such as acute pupillary enlargement, rapidly developing motor changes (over hours), or rapidly decreasing level of consciousness, are not eligible.
 20. Subjects with known allergic or hypersensitivity reactions to parenteral iron, parenteral dextran, parenteral iron-dextran, or parenteral iron-polysaccharide preparations (Ferumoxylol Investigator's Drug Brochure, 2009). *Subjects with significant drug or other allergies or autoimmune diseases may be enrolled at the investigator's discretion.*
 21. Subjects who have a contraindication for 3T MRI: metal in their bodies (a cardiac pacemaker or other incompatible device), are severely agitated, or have an allergy to gadolinium containing contrast material.
 22. Subjects with known iron overload (genetic hemochromatosis). In subjects with a family history of hemochromatosis, hemochromatosis must be ruled out prior to study entry with normal values of the following blood tests: Transferrin saturation (TS) test and Serum ferritin (SF) test. All associated costs will be paid by the study.
 23. Subject who have received ferumoxylol within 3 weeks of study entry.
 24. Subjects with three or more drug allergies from separate drug classes.

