7.5 Dose Modification

Adverse events (both non-serious and serious) associated with pembrolizumab exposure may represent an immunologic etiology. These adverse events may occur shortly after the first dose or several months after the last dose of treatment. Pembrolizumab must be withheld for drug-related toxicities and severe or life-threatening AEs as per Table 6 below.

Table 6 Dose Modification and Toxicity Management Guidelines for Immune-related AEs Associated with Pembrolizumab

General instructions:

Corticosteroid taper should be initiated upon AE improving to Grade 1 or less and continue to taper over at least 4 weeks. For situations where pembrolizumab has been withheld, pembrolizumab can be resumed after AE has been reduced to Grade 1 or 0 and corticosteroid has been tapered. Pembrolizumab should be permanently discontinued if AE does not resolve within 12 weeks of last dose or corticosteroids cannot be reduced to ≤ 10 mg prednisone or equivalent per day within 12 weeks. For severe and life-threatening irAEs, IV corticosteroid should be initiated first followed by oral steroid. Other immunosuppressive treatment should be initiated if irAEs cannot be controlled by corticosteroids.

Immune-related AEs	Toxicity grade or conditions (CTCAEv4.0)	Action taken to pembrolizumab	irAE management with corticosteroid and/or other therapies	Monitor and follow-up
Pneumonitis	Grade 2	Withhold	
 Administer corticosteroids (initial dose of 1-2 mg/kg prednisone or equivalent) followed by taper 	
 Monitor participants for signs and symptoms of pneumonitis Evaluate participants with suspected pneumonitis with radiographic imaging and initiate corticosteroid treatment Add prophylactic antibiotics for opportunistic infections
	Grade 3 or 4, or recurrent Grade 2	Permanently discontinue		

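### The immunosuppression clause of exclusion 3 is reversed: as written, the item bars no subject on continuous daily immunosuppression

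*Combined protocol and SAP*

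**What the plan says.** The list in Section 5.2 opens with "The subject must be excluded from participating in the trial if the subject", so meeting any item removes the subject. Item 3 is "Has a diagnosis of immunodeficiency and is not on continuous daily immunosuppressive therapy within 7 days prior to the first dose of trial treatment", followed in parentheses by "Subjects may receive steroids before or after SRS to prevent or manage cerebral edema; inhalational steroids are permitted".

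The item just above it, on EGFR and ALK aberrations, sits under the same lead-in but is worded as a condition the subject has to satisfy: "subject should have documented disease progression on FDA-approved therapy for these aberrations".

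Other text that bears on immunosuppression:

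- **Section 5.2, item 10:** "Has active autoimmune disease that has required systemic treatment in the past 2 years", with replacement therapy, including physiologic corticosteroids, not counted as systemic treatment.
- **Section 5.2, item 13:** "Has a history or current evidence of any condition, therapy, or laboratory abnormality that might confound the results of the trial", together with related grounds, in the treating investigator's opinion.
- **Section 4.7:** steroids may blunt the immune response, bevacizumab is preferred for edema, and subjects will be analysed separately by bevacizumab and steroid dose.
- **Section 7.5:** after an immune-related adverse event, pembrolizumab is stopped permanently if "corticosteroids cannot be reduced to ≤ 10 mg prednisone or equivalent per day within 12 weeks".
- **Sections 7.9 and 7.9.2:** drugs prohibited by the exclusion criteria are also prohibited on study.

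**The concern.** Eligibility items are applied literally at screening and audited literally afterwards. Under a lead-in that excludes whoever meets the item, the phrase 'is not on' makes absence of immunosuppression part of the ground for exclusion. An immunodeficient subject would stop meeting item 3 by taking daily immunosuppressants, and a subject without immunodeficiency could never meet it, whatever drugs they took.

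At stake is a safety and interpretability criterion for a checkpoint inhibitor. A screener who follows the words passes a continuously immunosuppressed subject on this item; one who follows the evident purpose fails the same subject. No other section states the intended rule, so the documents do not settle which of them is right.

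**Working it through.** The plan gives no figure on this point. The check is the logic of the item, then a comparison with the other rules that might close the gap.

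**Inputs.** The lead-in and item 3, both from Section 5.2. Let D be a diagnosis of immunodeficiency and S continuous daily immunosuppression in the 7 days before first dose. The item as written is 'D and not S'. The table compares it with each single-word correction and with both together.

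| D | S | As written: D and not S | 'or' only: D or not S | 'is on' only: D and S | Both: D or S |
|---|---|---|---|---|---|
| no | no | eligible | barred | eligible | eligible |
| no | yes | eligible | eligible | eligible | barred |
| yes | no | barred | barred | eligible | barred |
| yes | yes | eligible | barred | barred | barred |

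**Results.**

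- As written, the item bars 1 of 4 cases, and 0 of the 2 with S = yes.
- Changing only the conjunction bars 3 of 4, but one of these is the ordinary subject with neither condition, and it misses the subject with S alone.
- Changing only the negation bars 1 of 4 and misses both D alone and S alone.
- Both changes together bar 3 of 4, including 2 of the 2 with S = yes. The two cases whose status changes are (no, yes) and (yes, yes); the other two stay as they are.

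**Evidence of intent.** The parenthesis in item 3 permits peri-radiosurgery and inhaled steroids. That permission has work to do only if the item was meant to keep immunosuppressed subjects out. The remark in Section 4.7 about steroids blunting the immune response supports this, although it explains a preference for bevacizumab and sets no entry rule. The steroid limit in Section 7.5 governs adverse-event management, so it is indirect evidence only.

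**Do other entry rules close the gap?**

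- Item 8 (unresolved toxicity from an earlier agent) can catch a subject on steroids for a continuing immune toxicity. This matters because inclusion 6 admits prior PD-(L)1 users.
- Item 10 catches active autoimmune disease treated systemically in the past 2 years.
- Items 11, 12 and 16 catch non-infectious pneumonitis, active infection and HIV.
- Item 13 depends on opinion.

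None of the mandatory items reaches a subject on continuous immunosuppression for an unrelated reason. For example, no item mentions transplantation, so a subject on daily anti-rejection drugs who met no other exclusion could be kept out only under item 13.

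**Do the on-study rules close it?** Section 7.9 and the end of Section 7.9.2 point back to the exclusion list. The immune-suppressing part of Table 7 has 11 entries, all presented as natural or herbal supplements, and none is a conventional immunosuppressive drug. Section 7.9 also leaves the final decision on supportive therapy to the investigator or primary physician, so the on-study effect of the error is limited. The main defect is at entry.

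**The case against.** The strongest reply is that nobody would apply the literal rule. Item 2 is also a requirement placed under an exclusion lead-in. If the second half of item 3 is read the same way, as a requirement not to be on immunosuppression, the result is exactly 'D or S'. The steroid parenthesis points to the same reading, and a clinician screening for pembrolizumab is unlikely to treat immunosuppressants as making an immunodeficient patient acceptable.

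This stands as evidence of what was meant, and it makes misapplication less likely. It does not repair the rule: the literal and charitable readings give opposite answers for the same subject, and no text chooses between them.

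It is also fair that the plan expects steroid-treated subjects, since Section 4.7 commits to a separate analysis by steroid dose. That analysis does not cover non-steroid agents and says nothing about who may enter.

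A reader might infer that the whole criterion is inverted, or that the protocol has no control over immunosuppressed entrants. The documents support neither. Two of the four cases are handled correctly, and several mandatory items bar some immunosuppressed subjects on other grounds.

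**Conclusion.** The point holds for the immunosuppression clause. As worded, exclusion 3 bars none of the cases on continuous daily immunosuppression, contrary to the purpose its own steroid allowance shows. Immunodeficiency without immunosuppression remains barred and the ordinary subject remains eligible. After items 8, 10, 11, 12 and 16, what remains is the subject continuously immunosuppressed for an unrelated reason, for whom item 13 is the only check.

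The size is a count of logical cases (0 of 2 barred where 2 of 2 were meant), not of patients. The conclusion assumes that the lead-in governs item 3 as it does the rest of the list, and that the parenthesis reflects the drafters' intent.

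A reader might go further and infer that ineligible subjects were enrolled, or that the rCBV sensitivity and specificity are compromised. The documents give no enrolment data on this, and nothing in them links the wording to the accuracy estimates, the sample size or the Section 10 analyses. It should be fixed because an operative safety criterion says the opposite of its purpose.

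**What to change.** In Section 5.2, item 3, change 'and' to 'or' and 'is not on' to 'is on', keep the 7-day window, and begin the steroid parenthesis with the label 'Exception'. Both word changes are needed, as the table shows.

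The clinical team should confirm whether physiologic corticosteroid replacement, exempt under item 10, is also exempt here.

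Because Section 7.9 carries entry prohibitions into treatment, the corrected item would otherwise conflict with care the protocol itself directs or allows: Section 7.5 and Section 9.5.2 call for steroids, and Section 7.5 sometimes for other agents, in immune-related events, and Table 8 lists corticosteroids for infusion reactions. Add one sentence to Section 7.9: 'Corticosteroids or other immunosuppressants given for immune-related AEs or infusion reactions under Sections 7.5 and 9.5, and steroids for cerebral edema, remain permitted.'

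The cost is amendment wording in two sections, with no change to the sample size or the analysis.

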5.3 Subject Withdrawal/Discontinuation Criteria

Subjects may withdraw consent at any time for any reason or be dropped from the trial at the discretion of the investigator should any untoward effect occur. In addition, a subject may be withdrawn by the investigator or the Sponsor if enrollment into the trial is inappropriate, the trial plan is violated, or for administrative and/or other safety reasons.

A subject must be discontinued from the trial for any of the following reasons:

- The subject or legal representative (such as a parent or legal guardian) withdraws consent.
- Persistent radiographic progression confirmed by tissue biopsy.
- Persistent radiographic progression if subject is not a candidate for repeat surgery or subject refuses a repeat biopsy to pathological confirmed of disease progression

Note: A subject may be granted an exception to continue on treatment with confirmed radiographic progression if clinically stable or clinically improved, at the discretion of the treating physician. Please see Section 7.4.9

- Unacceptable adverse experiences as described in Section 9.0
- Miss two consecutive treatments for any reason other than surgery
- Intercurrent illness that prevents further administration of treatment
- Investigator's decision to withdraw the subject
- The subject has a confirmed positive serum or urine pregnancy test. If the urine test is positive, cannot be performed or cannot be confirmed as negative, a serum pregnancy test will be required. Noncompliance with trial treatment or procedure requirements
- The subject is lost to follow-up
- Completed 24 months of uninterrupted treatment with pembrolizumab or 35 administrations of study medication, whichever is later.

Note: 24 months of study medication is calculated from the date of first dose. Subjects who stop pembrolizumab after 24 months may be eligible for up to one year of additional study treatment if they progress after stopping study treatment provided they meet the requirements detailed in Section 5.4.1

- Administrative reasons

The End of Treatment and Follow-up visit procedures are listed in the Schedule of Events (Section 6). After the end of treatment, each subject will be followed for 30 days for adverse event monitoring (serious adverse events will be collected for 90 days after the end of treatment as described in Section 9). Subjects who discontinue for reasons other than progressive disease will have post-treatment follow-up for disease status until disease progression, initiating a non-study cancer treatment, withdrawing consent or becoming lost to follow-up. After documented disease progression each subject will be followed by telephone for overall survival until death, withdrawal of consent, or the end of the study, whichever occurs first.

5.3.1 Discontinuation of Study Therapy after CR

Discontinuation of treatment may be considered for subjects who have attained a confirmed CR in the brain and have been treated for at least 24 months with pembrolizumab.

At the discretion of the investigator, subjects who have had CR in the brain but develop progressive systemic disease may be eligible for up to one year of additional treatment with pembrolizumab via the Second Course Phase, if no additional cancer treatment was administered since the last dose of pembrolizumab, the subject meets the safety parameters listed in the Inclusion/Exclusion criteria, and the trial is open. Subjects will resume therapy at the same dose and schedule at the time of initial discontinuation. Additional details are provided in Section 7.4.9.

5.3.2 Subject Replacement Strategy

Subjects that are unevaluable will be replaced. Subjects that are unevaluable are those who do not reach the first follow-up imaging time point (12 weeks after first pembrolizumab infusion).

5.3.3 Clinical Criteria for Early Trial Termination

Early trial termination will be the result of the criteria specified below:

1. Quality or quantity of data recording is inaccurate or incomplete
2. Poor adherence to protocol and regulatory requirements
3. Incidence or severity of adverse drug reaction in this or other studies indicates a potential health hazard to subjects
4. Plans to modify or discontinue the development of the study drug

In the event of Merck decision to no longer supply study drug, ample notification will be provided so that appropriate adjustments to subject treatment can be made.

Product: Pembrolizumab

39

Protocol/Amendment No.: #7 Date: 3/31/2022

¹Brain surgery is not necessary before enrollment. However, a brain surgery may be done prior to enrollment or at the time of persistent radiographic progression if clinically indicated. Pembrolizumab needs to be stopped for 4 weeks prior to and will not be restarted for at least 4 weeks after surgery (section 7.2). All tissue will be sent for biomarkers.

²Physical exam only required with every pembrolizumab infusion.

³CBC and CMP to be done with every cycle while on pembrolizumab – labs must be done within 30 days before first pembrolizumab infusion, and within 72 hours before subsequent infusions.

⁴ FT4 and TSH with every cycle while on pembrolizumab

⁵Clinical standard of care MRIs (gadolinium with perfusion) are done at baseline, 12 weeks post radiation, then every 9 weeks, and 6 weeks after suspected radiographic progression (see special instructions below for evaluating persistent radiographic progression). All timepoints are ± 15 days. Clinical scans may be done more frequently, at physician's discretion. Each MRI scan will be evaluated for progression.

⁶Ferumoxytol steady state MRIs (within 10 days of clinical standard of care MRIs) are done baseline, 12 weeks post radiation, anytime there is suspected radiographic progression and 6 weeks after suspected radiographic progression. All timepoints are ± 15 days. Serum biomarkers will be obtained ± 15 days of ferumoxytol MRI scan.

⁷ Follow-up after completing 2 years of treatment or 32 cycles (whichever comes later): clinical standard of care MRI and clinical visit every 12 weeks ($+30$ days) for up to 1 year, and every 6 months ($+30$ days) until death.

⁸ Survival follow-up once off study: Telephone contact every 12 weeks ($+30$ days) to assess for survival status until death, withdrawal of consent, the end of the study, or loss to follow-up, whichever occurs first.

⁹Evaluation of systemic disease burden: A standard of care PET /CT or CT abdomen, chest and pelvis with contrast will be obtained within 3 months of enrollment and every 6 months while on study thereafter.

¹⁰Adverse event review will be recorded in Epic continuously while on study. A separate Epic note will be done with each course. All AEs are assessed for attribution to pembrolizumab, ferumoxytol, and standard of care therapy.

¹¹ First dose of pembrolizumab will be given on the first day of radiation (± 15 days), and every 3 weeks thereafter ($+15$ days).

Imaging instructions for evaluating persistent radiographic progression: if there is suspected progression, subjects undergo a ferumoxytol steady state MRI and continue on pembrolizumab for two more cycles (total of 6 weeks). At the 6 week point, clinical standard of care and ferumoxytol MRIs will be repeated to confirm persistent radiographic progression. If the 6 week scan confirms progression, then pembrolizumab is discontinued and subject is evaluated for surgery. If histopathology confirms pseudoprogession or is inconclusive, the subject will continue on pembrolizumab every 3 weeks until further radiographic progression is

Product: Pembrolizumab

40

Protocol/Amendment No.: #7 Date: 3/31/2022

suspected. If histopathology confirms progression, the subject will be removed from the study. If the subject is not a surgical candidate, they will be taken off study and move into the survival follow up stage.

7.0 TREATMENT PLAN AND PROCEDURES

The Schedule of Events - Section 6.0 summarizes the trial procedures to be performed at each visit. Individual trial procedures are described in detail below. It may be necessary to perform these procedures at unscheduled time points if deemed clinically necessary by the investigator.

Furthermore, additional evaluations/testing may be deemed necessary by the Sponsor and/or Merck for reasons related to subject safety. In some cases, such evaluation/testing may be potentially sensitive in nature (e.g., HIV, Hepatitis C, etc.), and thus local regulations may require that additional informed consent be obtained from the subject. In these cases, such evaluations/testing will be performed in accordance with those regulations.

